1. REVISION HISTORY

Version	Date	Revision Author	Comments
1.0	04JAN2018		Original SAP
1.1	11DEC2018	[REDACTED]	Update stratification factors and response definitions for “Time of Return to Ability to Perform Normal Activities” and “Time of Return to Usual Health” in accordance with protocol v1.5
1.2	TBD	[REDACTED]	Update to: 
 1. Clarify handling of missing concomitant medications end dates and times of dosing (Section 8.4); 2. Add protocol deviation category “GCP” (Sections 9.1.2, 9.2); 3. Remove subject initials and urine pregnancy test result from Demographic Data listing (Section 9.1.2); 4. Clarify definition of “time from symptom onset” to mean the time in hours between the time of first dose of study medication and the patient-reported time of symptom onset (Sections 9.1.4, 10.2, 10.2.2, 10.4.1, 10.4.3, 10.5.1 - 10.5.4); 5. Clarify source of time of first dose data (Sections 10.2, 10.4.1, 10.4.3, 10.5.1 - 10.5.4); 6. Update cumulative distribution parameters for selection of maximum symptom response criteria from 75%-90% to 90%-95% (Section 10.2.1); 7. Update procedure for selection of maximum symptom response criteria where the number of daily diary records to be evaluated exceeds the capacity of the IT system (Section 10.2.1); 8. Clarify maximum symptom response criteria including improvement of example case (Section 10.2.1); 9. Clarify impact of symptom relief medication use on Time to FLU-PRO Domain Response and Resolution of Acute Febrile Illness analyses (Sections 10.5.2, 10.5.3); 10. Specified that the primary and secondary efficacy analyses will be analyzed in a hierarchical fashion (Section 10.4); and 11. Clarified derivation of analysis variables for analysis of Proportions of Subjects with Detectable Virus at Days 2, 3 and 7 (Section 10.5.6).

3. TECHNICAL SUMMARY REPORT

Name of Sponsor/Company: The Romark Institute for Medical Research	Individual Study Table Referring to Part of the Dossier:	For National Authority Use Only
Name of Finished Product: Nitazoxanide 300 mg Tablets	Volume:	
Name of Active Ingredient: Nitazoxanide	Page:	
Title Of Study: A Phase III Randomized, Double-Blind. Placebo Controlled Trial to Evaluate the Efficacy and Safety of Nitazoxanide in the Treatment of Uncomplicated Influenza		
Investigators: Multicenter		
Studied period: December 2017 – April 2019		Phase of development: III
Objectives: 
The primary objective of this study is to evaluate the effectiveness of nitazoxanide (NTZ) administered orally 600 mg b.i.d. with food for 5 days in reducing the duration of symptoms of influenza compared to that of a placebo during 21 days of follow up based upon the FLU-PRO[®] patient-reported outcome instrument.
 
A key secondary efficacy objective is to evaluate the effect of NTZ compared to placebo on time to return to ability to perform all normal activities.
 
Other secondary efficacy objectives include evaluating the effect of NTZ compared to placebo on:
 
 a) the proportion of subjects experiencing one or more complications of influenza including pneumonia, otitis media, bronchitis, sinusitis, worsening of pre-existing health conditions, systemic antibiotic use for infections secondary to influenza infection, hospitalization due to complications of influenza, and death; and b) the duration of symptoms of influenza during 21 days of follow up based upon the four FLU-PRO domains (Body/Systemic, Throat, Chest/Respiratory and Nose) that correspond to the seven symptoms included in the traditional patient-reported outcomes instrument (feverishness, myalgia, headache, fatigue, sore throat, nasal obstruction and cough). 
Other important objectives include evaluation of the safety of NTZ by analysis of adverse events and effect on influenza antibody titers.
		
Number of Subjects: A sample size of at least 600 (up to a maximum of 700) subjects with laboratory-confirmed influenza is planned for the study. This is estimated to require approximately 800 to 1200 subjects in total.		
Study Design: Multicenter randomized double-blind placebo controlled trial for evaluation of efficacy and safety of NTZ in the treatment of uncomplicated influenza		
Population: Males and females ≥12 years of age with uncomplicated influenza		

Study Dose and Administration:

Group 1 (NTZ): Two NTZ 300 mg tablets orally twice daily (b.i.d.) with food for 5 days.

Group 2 (Placebo): Two placebo tablets orally b.i.d. with food for 5 days.

5. LIST OF ABBREVIATIONS

AE	Adverse event
ALT	Alanine aminotransferase
AST	Aspartate aminotransferase
b.i.d.	Twice daily
BUN	Blood urea nitrogen
CSR	Clinical study report
EDC	Electronic data capture
FDA	U.S. Food and Drug Administration
GGT	Gamma-glutamyl transferase
HDL	High density lipoprotein
hMPV	Human metapneumovirus
LDL	Low density lipoprotein
LLN	Lower limit of normal
MedDRA	Medical Dictionary for Regulatory Activities
NTZ	Nitazoxanide
RSV	Respiratory syncytial virus
RT-PCR	Reverse transcriptase polymerase chain reaction
SAE	Serious adverse event
SAP	Statistical analysis plan
SOC	System organ class
T	Tizoxanide
TCID ₅₀	Tissue culture 50% infective dose
TEAE	Treatment-emergent adverse event
TG	Tizoxanide glucuronide
ULN	Upper limit of normal

6. INTRODUCTION

The purpose of this statistical analysis plan (SAP) is to describe the planned analyses and data displays to be included in the Clinical Study Report (CSR) for Protocol RM08-3004.

All decisions regarding final analysis as defined in this SAP will be made prior to unblinding of the study data. Further information can be found in the protocol.

The SAP is based on:

- Protocol RM08-3004, Final Version 1.5, December 12, 2018
- International Conference on Harmonisation Guidelines E4 and E9; and
- Discussions with the U.S. Food and Drug Administration (FDA).

The purpose of this document is to describe analysis populations and to detail methodology for deriving variables, handling missing data, and analyzing efficacy and safety data.

The SAP may be revised or amended to reflect the requirements of protocol amendments or regulatory requests, but must be finalized, approved and placed on file before the database is locked. Deviations from the SAP will be noted in the CSR.

7. STUDY DESCRIPTION

7.1 Study Objectives

The primary objective of this study is to evaluate the effect of nitazoxanide (NTZ) administered orally 600 mg b.i.d. with food for 5 days in reducing the duration of symptoms of influenza compared to that of a placebo.

A key secondary efficacy objective is to evaluate the effect of NTZ compared to placebo on time to return to ability to perform all normal activities.

Other secondary efficacy objectives include evaluating the effect of NTZ compared to placebo on:

- a) the proportion of subjects experiencing one or more complications of influenza including pneumonia, otitis media, bronchitis, sinusitis, worsening of pre-existing health conditions, systemic antibiotic use for infections secondary to influenza infection, hospitalization due to complications of influenza, and death; and
- b) the duration of symptoms of influenza during 21 days of follow up based upon the four FLU-PRO domains (Body/Systemic, Throat, Chest/Respiratory and Nose) that correspond to the seven symptoms included in the traditional patient-reported outcomes instrument (feverishness, myalgia, headache, fatigue, sore throat, nasal obstruction and cough).

Exploratory efficacy objectives include evaluating the effect of treatment with NTZ on the time to response for each FLU-PRO symptom, time to response for each FLU-PRO domain, time to resolution of febrile illness, time to return to usual health, and changes in viral titers from baseline to each of days 2, 3 and 7.

Other important objectives include evaluation of the safety of NTZ by analysis of adverse events and evaluation of the effect of nitazoxanide on influenza antibody response and evaluation of relationships between pharmacokinetics and clinical or virologic responses.

7.2 Study Design

The study will be a multicenter, randomized, double-blind trial to evaluate the efficacy of NTZ compared to placebo in treating uncomplicated influenza. Subjects will be selected according to the inclusion and exclusion criteria listed in the protocol. The study is designed to enroll at least 600 subjects (up to 700 maximum) with laboratory-confirmed influenza. Total enrollment required to achieve this number is expected to be approximately 800 to 1200 subjects. Prior to screening for inclusion in the study, informed consent will be obtained.

Immediately after completion of informed consent, screening, and enrollment in the study, two baseline nasopharyngeal swabs will be collected for viral culture and RT-PCR. A blood sample will be collected for laboratory safety tests and anti-influenza antibodies, and a urine sample will be collected for laboratory safety tests. Subjects will receive instruction on completing their electronic diaries, recording concomitant medications and attending follow-up visits.

Then subjects will be randomized 1:1 to one of the following groups:

- Group 1 (NTZ): Two NTZ 300 mg tablets b.i.d. for 5 days
- Group 2 (Placebo): Two placebo tablets b.i.d. for 5 days

The medication will be taken in the morning and evening with food. The first dose will be taken with food in the physician's office under the observation of the Principal Investigator or a member of the Investigator's staff. The second dose will be taken by the patient as close as possible to 12 hours after the first dose.

A nurse or other study personnel will visit each subject (or the subject will return to the clinic) on study days 2 and 3 to collect two nasopharyngeal swabs, to review patient diaries, and to review symptoms and screen for influenza-related complications including sinusitis, otitis, bronchitis, pneumonia and central nervous system disease. Subjects will be referred for immediate care as needed based on the screening. A blood sample for pharmacokinetics will also be collected on study day 3. These day 2 and 3 visits will occur at approximately the same time of day that the subject took his/her first dose of study medication (roughly 24 and 48 hours post-first dose). On day 3, the blood sample for pharmacokinetics will be collected before the dose. The nasopharyngeal swabs will be used to evaluate quantitative changes in viral shedding. The blood samples will be used to evaluate relationships between pharmacokinetics and virologic or clinical response. Study sites or subjects may opt out of the day 2 and day 3 visits due to site staffing, patient availability or other practical considerations or preferences; nevertheless, at least 75% of subjects enrolled in the trial are expected to complete the day 2 and day 3 visits and related procedures (for viral kinetics and pharmacokinetics).

A study physician, nurse or other site personnel will make daily telephone calls to subjects for the first five days of dosing to review symptoms and screen for influenza-related complications including sinusitis, otitis, bronchitis, pneumonia and central nervous system disease. Subjects will be referred for immediate care as needed based on the screening. [Note: In lieu of a telephone call, this information may be obtained during the day 2 or 3 office or home visits (see the preceding paragraph).] The study sites and subjects will be blinded from virology laboratory data until after study day 22 or, if earlier, until the subject is discontinued from the study. During the study period,

each subject will be presumed to have influenza infection, and any worsening of symptoms or complications will be presumed to be influenza-related.

[figure not shown]
Subjects will return to the clinic on days 7 and 22 for post-treatment follow-up, including two nasopharyngeal swabs, drug accountability, reporting of adverse events and complications of influenza. Blood and urine samples for laboratory safety tests will be collected at day 7, and a blood sample for anti-influenza antibodies will be collected on day 22. A nurse or other study personnel will review the electronic patient diary entries daily (synchronized to a web-based data system) to ensure contemporaneous and complete recording of diary data. Subjects will maintain the electronic patient diaries until study day 22. Any visits that do not occur on the prescribed date, or within 1 day of that date in the case of the day 7 visit or within 3 days after in the case of the day 22 visit will be recorded as protocol deviations.

A central laboratory will be used for laboratory safety tests, anti-influenza antibodies and virology testing. Laboratory safety tests will include hemoglobin, hematocrit, complete blood count (total and differential), platelet count, random blood sugar, total cholesterol, HDL, LDL, triglycerides, albumin, AST, ALT, GGT, alkaline phosphatase, bilirubin (total/direct), BUN, creatinine, sodium, potassium, chloride and routine urinalysis (glucose, protein and blood). Virology testing will include RT-PCR assay to identify influenza A (non-specific as to subtype); influenza A H1, H3 and H1N1 (2009) subtypes; influenza B; respiratory syncytial virus A and B (RSV); parainfluenza 1, 2, 3 and 4; human metapneumovirus (hMPV); adenovirus; human rhinovirus/enterovirus; coronavirus NL63, HKU1, 229E and OC43; human bocavirus; *Chlamydomphila pneumoniae*; *Legionella pneumophila*; and *Mycoplasma pneumoniae* (baseline and day 7 nasopharyngeal swabs), culture (baseline and day 7 nasopharyngeal swabs), and quantitation of influenza viruses by TCID₅₀ (baseline and days 2, 3 and 7 nasopharyngeal swabs). Follow-up samples (days 2, 3 and 7) collected from subjects who do not test positive for influenza A or influenza B at baseline will not be analyzed for quantitative influenza viral titer.

This study is expected to run from December 2017 through April 2019.

7.3 Sample Size Justification

The Symptom Response definition for this study will be derived from the subjects' FLU-PRO questionnaire responses as described in section 10.2.1 below. The FLU-PRO-derived endpoint is expected to track very closely to return to usual health status (a daily yes/no question in the FLU-PRO questionnaire). Patient-reported outcomes for time to return to usual health status have been shown to track very closely with time to ability to perform 100% of usual activities.^{1,2,3} We assume, therefore, that the cumulative distributions of time to symptom response for the placebo treatment group will closely reflect historical data (Romark studies RM08-3002 and RM08-3003 and oseltamivir studies WV15670 and WV15671) for time from first dose until the subjects report that they are able to perform 100% of usual activities. Based upon data from Romark studies RM08-3001, RM08-3002 and RM08-3003, we assume that treatment with NTZ should result in reduction of at least 40 hours in median time to symptom response with differences being less at the first quartile and greater at the third quartile. Based upon this historical data, the following curves have been developed for determining sample size.

Based upon these curves, a sample size of 552 subjects with laboratory-confirmed influenza (i.e. 276 for each of the 2 groups) will provide 90% power to detect a statistically significant difference in the survival distributions between NTZ and placebo groups (2-sided alpha of 0.05). This calculation was performed for the Gehan rank test using SAS PROC POWER (SAS 9.4) with the curves shown above (proportion not recovering by the end of each day was used as input) and censoring at day 21 (hour 504). Assuming that 8% of subjects will have incomplete data, we arrive at a sample size of 600 subjects in total, 300 per treatment group.

Based upon these calculations, the study will enroll at least 600 subjects with laboratory-confirmed influenza up to a maximum of 700 subjects with laboratory-confirmed influenza. We estimate that this will require enrollment of 800 to 1,200 subjects in total assuming a flu-positive rate between 50% and 75%.

7.4 Data Collection

Data will be collected using an electronic data capture (EDC) system and electronic subject diaries provided by Clinical Ink, Inc.

Medical history and adverse events will be coded using the latest version of MedDRA. Prior and concomitant medications will be coded using the latest version of WHODrug.

8. DATA DEFINITIONS AND CONVENTIONS

8.1 Analysis Populations

Three populations will be designated for the purpose of these analyses:

Table 1. Definition of Analysis Populations

Analysis Population	Definition
All Treated	All subjects who receive at least one dose of study medication
Confirmed Influenza	The subset of the All Treated population who are positive for influenza by RT-PCR or culture at any of the Baseline, Day 2 or Day 3 visits
Per Protocol	The subset of the Confirmed Influenza population with no major protocol deviations that may have an effect on the integrity of the data or the evaluation of effectiveness

8.2 Data Presentation Conventions

The following conventions are applied to all data presentations and summaries.

Table 2. Data Presentation Conventions

Data	Presentation Convention
Descriptive statistics for continuous variables	Include the number of subjects with available data, mean, standard deviation, median, minimum and maximum values
Descriptive statistics for categorical variables	Include a count of subjects with each response and percentage of subjects with each response out of the total number of subjects per population or treatment group, as applicable
Means and medians for continuous variables	Format to one more decimal place than the measured value
Standard deviations for continuous variables	Format to two more decimal places than the measured value
Minimums and maximums for continuous variables	Format to the same number of decimal places as the measured value
Number and percent for categorical variables	XX (XX.X%)
Date variables	DDMMMYYYY
Time variables	HH:MM (24-hour clock)
P -values	Present five decimal places If less than 0.00001, present as <0.00001 If rounded result is 1.00000, present as >0.99999
All decimal-containing data, where possible	Presentation should be decimal-aligned
Data presented by visit	Summarize by nominal study visit
Randomization groups	Present as “NTZ” and “Placebo” in that order

The expected layout of each table, listing and figure will be approved separately from the SAP. Minor changes to titles or numbering will not necessitate a revision of the SAP nor will they be considered deviations from the planned analyses.

8.3 Handling of Unscheduled Assessments

Results of unscheduled assessments will be included in listings, but will not be used in descriptive statistics.

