5.8 Unscheduled Visit

Subjects returning to the clinic for an unscheduled visit due to worsening symptoms or adverse events will be evaluated at the discretion of the Investigator as is medically warranted. Tests and/ or procedures performed at this visit may include, but are not limited to the following.

- 1) Physical examination. Brief physical examination (body weight and vital signs with nursing physical assessment) including symptom directed physician physical examination as required by patient symptoms. Vital signs will include blood pressure, pulse, respiratory rate and oral temperature (use standard electronic oral thermometer provided by Sponsor);

- 2) Collection of two nasopharyngeal swabs using nylon flocked dry swabs (Copan Diagnostics) for RT-PCR and culture;
- 3) Collection of blood sample for laboratory safety tests including hemoglobin, hematocrit, complete blood count (total and differential), platelet count, random blood sugar, total cholesterol, HDL, LDL, triglycerides, albumin, AST, ALT, GGT, alkaline phosphatase, bilirubin (total/direct), BUN, creatinine, sodium, potassium, chloride;
- 4) Collection of urine sample for routine urinalysis (glucose, protein and blood);
- 5) Review of compliance with study medication;
- 6) Review and recording of concomitant medications; and
- 7) Review and recording of adverse events/side effects.

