5.9 Study Discontinuation

Rules for discontinuation of a patient or for discontinuing the study are provided in section 11.2. All subjects discontinued from the study before day 7 will be evaluated at study discontinuation using the procedures described above for day 7. All subjects discontinued from the study after day 7 will be evaluated at study discontinuation using the procedures described above for day 22.

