10.2 Clinical Adverse Events

At the time of each return visit, the subject will be questioned regarding the occurrence and nature of any adverse events. All events must be recorded in the subjects' medical records and in the EDC system. Any subject affected will be examined by the Investigator as deemed necessary to ascertain the course of the event and any residual effects.

All moderate and severe adverse events will be reviewed by the Principal Investigator who will determine using his/her best clinical judgment whether they warrant the subject to be discontinued from the study. The Sponsor will be notified immediately if a subject is discontinued from the study. For all adverse events that require the subject to be discontinued from the study, relevant clinical assessments and laboratory tests will be repeated as clinically indicated until final resolution or stabilization of the event(s).

All subjects will be instructed to contact the Investigator, Investigator's assistants, or clinical personnel should the subject have any serious adverse experiences. Serious adverse events (SAEs), including death regardless of the cause, must be reported to the Sponsor immediately (within 24 hours of the initial report).

A serious event requiring immediate notification by telephone is an event that:

- results in death
- is life threatening
- requires inpatient hospitalization or prolongation of an existing hospitalization
- is a persistent or significant disability/incapacity
- is a congenital anomaly/birth defect
- an important medical event that may not result in death, be life-threatening, or require hospitalization but, based upon appropriate medical judgment, may jeopardize the subject and may require medical or surgical intervention to prevent one of the outcomes listed above.

An overdose is defined as any intentional or unintentional consumption of the drug by any route that exceeds the highest dose stated in the Investigator's Brochure or in an investigational protocol, whichever dose is larger. Overdoses without an associated adverse event should be recorded, but not reported as an adverse event.

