11.1.3 Laboratory Results and Changes from Baseline

Numerical hematology and serum biochemistry values will be converted to SI units and classified as Normal, Grade 1, Grade 2, Grade 3 or Grade 4 according to reference ranges indicated in the protocol toxicity grading scale tables (see Appendix II). Urinalysis results will be classified as Normal or Abnormal based on reference ranges provided by the central laboratory.

Hematology, serum biochemistry, and urinalysis laboratory results and change from Baseline will be summarized using descriptive statistics for each visit.

Shift tables will display shifts from Baseline in laboratory results classification (Grade 1/2/3/4 or Normal/Abnormal) by study day.

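### Laboratory and vital-sign results from unscheduled visits reach only the listings, and no worst post-baseline table is planned to bring them back into the safety tables

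*SAP*

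**What the plan says.** **Rule for unscheduled results.** SAP 8.3 reads: "Results of unscheduled assessments will be included in listings, but will not be used in descriptive statistics". The sentence covers all data types.

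**Presentation conventions (SAP 8.2, Table 2).** For data presented by visit: "Summarize by nominal study visit". Descriptive statistics for categorical variables are defined thus: "Include a count of subjects with each response and percentage of subjects with each response".

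**Laboratory and vital-sign tables.** SAP 11.1.3: "Hematology, serum biochemistry, and urinalysis laboratory results and change from Baseline will be summarized using descriptive statistics for each visit". It continues: "Shift tables will display shifts from Baseline in laboratory results classification", arranged by study day. SAP 11.1.4 does the same for vital signs. SAP Appendix II lists displays 14.3.2.1 to 14.3.5.2 for these data, and none is a worst post-baseline or any-time table.

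**Where off-schedule results come from.** Protocol 5.8: "Subjects returning to the clinic for an unscheduled visit due to worsening symptoms or adverse events will be evaluated"; vital signs, safety blood tests and urinalysis are among the procedures it names. Protocol 10.2, for adverse events that lead to discontinuation: "relevant clinical assessments and laboratory tests will be repeated as clinically indicated", continuing until the event resolves or stabilizes. Protocol 5.9: "All subjects discontinued from the study before day 7 will be evaluated at study discontinuation using the procedures described above for day 7"; after Day 7 the Day 22 procedures apply.

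**The concern.** An unscheduled sample is usually taken because something has gone wrong, so leaving such samples out of the tables is a selective omission. In this trial little else can show the same abnormality, because Day 7 is the only scheduled safety laboratory time point after baseline. Suppose a subject has a Grade 3 value at an unscheduled visit before Day 7 and a lower grade at Day 7. On the natural reading of the SAP, that subject appears in the laboratory shift table with the lower grade only.

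What is at stake is how completely the laboratory and vital-sign tables describe safety. These tables are meant to give a view that does not depend on an investigator deciding to report an event. No independent data monitoring committee looks at the data (Protocol 14), so the tables in the study report carry more of that weight.

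**Working it through.** The plan gives no figure on this point to reproduce. The check is mainly a comparison of sections.

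**1. Scheduled post-dose data** (Protocol 5.6, 5.7 and Appendix I).
- Safety blood and urine: Day 7 only. Day 22 has none.
- Vital signs: Day 7 and Day 22.

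**2. Other post-dose data, and whether the tables use them.**
- Protocol 5.8 visits: unscheduled by name, with their own column in the schedule. SAP 8.3 excludes them.
- Protocol 10.2 repeat tests: taken as needed. The SAP assigns them to no nominal visit, so a by-visit table has no place for them unless they fall at a scheduled visit.
- Protocol 5.9 discontinuation evaluations: not called unscheduled. The SAP has no early-termination visit and no mapping rule, so their place is unstated.

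**3. Does SAP 8.3 reach the shift tables?** Table 2 treats counts and percentages of categories as descriptive statistics, and a grade-shift table consists of such counts. The exclusion therefore applies on the natural reading, although SAP 11.1.3 does not say so outright. Even on the other reading, no display gives each subject's worst grade.

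**4. Do the listings make up for it?** SAP 11.2, Table 6, gives laboratory listings a class of L/N/H, and the vital-signs listing no class at all. Toxicity grades are planned only for the tables. The grade of an unscheduled value therefore appears in no planned laboratory or vital-sign output.

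**5. Do the adverse-event tables make up for it?** In part. SAP 11.1 counts each subject at maximum grade, whatever the visit. Under Protocol 10, however, a laboratory change is an adverse event only if judged clinically significant. Symptoms and complications of influenza are not adverse events unless study medication caused them.

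**6. Size, by illustration only.** The documents give no rate of unscheduled visits or of Grade 3 or higher abnormalities. Let p be the true share of subjects with such an abnormality, and u the share of those subjects in whom it is seen only at results that the tables do not use. Then

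tabulated share = p × (1 − u).

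Take 800/2 = 400 to 1,200/2 = 600 treated subjects per arm, and assume u between 10% and 50%:

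| assumed p | tabulated, u = 50% | tabulated, u = 10% |
|---|---|---|
| 1% | 0.5% | 0.9% |
| 3% | 1.5% | 2.7% |
| 5% | 2.5% | 4.5% |

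At p = 3% and u = 50%, 400 × 0.03 = 12 subjects become 6, and 600 × 0.03 = 18 become 9.

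The ratio between arms is multiplied by (1 − u for NTZ)/(1 − u for placebo). With both values between 10% and 50%, this factor runs from 0.50/0.90 = 0.56 to 0.90/0.50 = 1.80. Bias in either direction is possible, and equal u in both arms leaves the ratio unchanged.

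**The case against.** The strongest reply is that little is lost. Safety analysis is descriptive, every value stays in a listing, and adverse events are recorded at unscheduled visits. The Protocol 10.2 repeats follow adverse events that are already on record, and these events appear in the adverse-event tables at maximum grade, with separate tables for Grade 3 or higher and for withdrawal. The fortnightly safety review in Protocol 11.1 uses adverse-event listings and does not depend on SAP 8.3. All of this stands, and it limits the consequence. It does not restore the numeric results or their grades to the laboratory and vital-sign tables.

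Three stronger readings are tempting, and the documents support none of them.

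- A reader might infer that samples from subjects who stop or withdraw are dropped. Protocol 5.9 makes the discontinuation evaluation a separate, required one using Day 7 or Day 22 procedures, and it may well be tabulated under those labels. The defect there is a missing mapping rule. After Day 7 that evaluation includes no safety laboratory sample.
- A reader might infer that any abnormality outside Days 6 to 8 is absent from the shift tables. That is wrong for vital signs, which are also scheduled at Day 22. It is also wrong for a nominal Day 7 visit held out of window: that visit is a protocol deviation but keeps its nominal label.
- A reader might infer that the tables will hide toxicity on NTZ in particular. Nothing supports a direction. Unscheduled visits are also prompted by worsening illness, which may be as common or more common on placebo. Protocol 1.2.7 reports no laboratory abnormalities attributed to the drug in earlier trials.

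**Conclusion.** The point holds for the laboratory and vital-sign tables. Results from Protocol 5.8 visits, and Protocol 10.2 repeats that fall at no scheduled visit, are kept out by rule. No worst post-baseline display brings them back, and the listings do not grade them. For by-visit summaries this follows directly from SAP 8.3. For shift tables it rests on reading Table 2's definition of descriptive statistics into SAP 8.3, which is the natural reading but not an explicit statement.

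The size cannot be known from the documents. The illustrated loss of 10% to 50% of Grade 3 or higher cases is an assumption, and the direction between arms is open. The primary and secondary efficacy analyses and the power are not affected. This is a worthwhile and cheap improvement to safety reporting, not a flaw that threatens the trial's main conclusion. The SAP already counts adverse events at maximum grade, so the change extends its own principle to laboratory and vital-sign data.

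**What to change.** Amend SAP 8.3, 11.1.3 and 11.1.4 before database lock, as SAP 6 allows:

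- Keep by-visit summaries and changes from baseline on scheduled visits only.
- Add a shift from baseline to worst post-baseline grade that uses all post-dose assessments, scheduled or not, or base displays 14.3.2.2, 14.3.3.2 and 14.3.5.2 on that shift.
- For urinalysis (14.3.4.2), which SAP 11.1.3 classes only as normal or abnormal, use any post-baseline abnormal result.
- State that Protocol 5.9 discontinuation evaluations count in the worst post-baseline tables whatever visit label they carry.

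No new data are needed. The cost is SAP wording and minor extra programming, and the reported rates of abnormal values may be slightly higher.
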